8.1.2.1. Laboratory Test Abnormalities

Laboratory abnormalities that constitute an AE in their own right (i.e., are considered to be clinically significant, induce clinical signs or symptoms, require concomitant therapy, or require changes in study treatment), should be recorded on the Adverse Events CRF. Whenever possible, a diagnosis, rather than a symptom should be provided (e.g., anemia instead of low hemoglobin). Laboratory abnormalities that meet the criteria for an AE should be followed until they have returned to normal or an adequate explanation of the abnormality is identified. When an abnormal laboratory or test result corresponds to a sign/symptom of an already reported AE, it is not necessary to separately record the laboratory/test result as an additional event.

A laboratory abnormality that does not meet the definition of an AE should not be reported as an AE. A Grade 3 or 4 event (severe per NCI CTCAE v4.03) does not automatically indicate an SAE unless it meets the definition of serious as defined in Section 8.1.1 and/or as per Investigator's discretion. A laboratory abnormality that results in a dose being held or modified would, by definition, be an AE and must be recorded as such in the eCRFs.

8.1.3. Adverse Event Severity

The severity of the AE will be graded by the Investigator according to the NCI CTCAE Grading Scale, v. 4.03 (the NCI CTCAE files can be accessed online at the following URL: <http://evs.nci.nih.gov/ftp1/CTCAE/About.html>).

If NCI CTCAE grading does not exist for an AE, the severity will be characterized as "mild," "moderate," "severe," or "life-threatening" (corresponding to Grades 1 to 4) according to the following definitions:

- Mild events are usually transient and do not interfere with the patient's daily activities.
- Moderate events introduce a low level of inconvenience or concern to the patient and may interfere with daily activities.
- Severe events interrupt the patient's usual daily activities.
- Life-threatening.

The term "severe" is used to describe the intensity of an AE; the event itself could be of relatively minor clinical significance (e.g., 'severe' headache). This is not the same as a "serious" AE.

8.1.4. Adverse Event Causality

The Investigator will make a judgment regarding the relationship of the AE to study treatment, as outlined in Table 20.

Table 20: Classification of Adverse Events by Causality

Not related	The lack of a temporal relationship of the event to the study treatment makes a causal relationship not reasonably possible, or other drugs, therapeutic interventions, or underlying conditions provide a sufficient explanation.
Related	The temporal relationship of the event to the study treatment makes a definitive relationship, and the event is more likely explained by exposure to the study treatment than by any other drugs, therapeutic interventions, or underlying conditions.

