6.2.6.2. Dose-Limiting Toxicity

A DLT is defined as an AE or abnormal laboratory value that occurs within the first 28 days of treatment with KPT-9274, except for those that are clearly and incontrovertibly due to underlying disease, disease progression, or extraneous causes, and meets any of the criteria included in [Table 14](#). The CTCAE, Version 4.03 will be used for grading. In addition, > 3 missed (consecutive or non-consecutive) doses of KPT-9274 in the first 28 days due to a drug related toxicity will be considered to be a DLT.

Other events may occur which do not meet the definition of a DLT, but are of concern to the Investigators and Karyopharm, and may then be considered to be DLTs.

Table 14: Criteria for Defining Dose-Limiting Toxicities

Toxicity	Any of the following criteria (based on CTCAE [Version 4.03]):
Non-Hematologic	Grade \geq 3 nausea/vomiting, dehydration or diarrhea while taking optimal supportive medications.
	Any other Grade \geq 3 non-hematological toxicity except alopecia or electrolyte abnormalities correctable with supportive therapy.
Hematologic	Grade 4 neutropenia lasting more than 5 days.
	Febrile neutropenia of any duration (ANC $< 1.0 \times 10^9$ with single temperature $> 38.3^{\circ}\text{C}$ or a sustained temperature $\geq 38^{\circ}\text{C}$ for more than 1 hour).
	Grade 4 thrombocytopenia, or Grade 3 thrombocytopenia with bleeding, or any requirement for platelet transfusion.
	Grade 4 anemia, unexplained by underlying disease.

CTCAE Version 4.03 will be used for grading AEs and laboratory abnormalities. Patients may receive supportive care as per local institutional guidelines.

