8.2.2. Reporting of Serious Adverse Events

Every SAE, regardless of the causal relationship to the study treatment, occurring after the patient has signed informed consent, until at least 30 days after the patient has stopped study treatment, must be reported to the Karyopharm Pharmacovigilance Department within *24 hours* of learning of its occurrence. The investigational site personnel must use the SAE Report Form provided by Karyopharm for reporting any SAE to the Karyopharm Pharmacovigilance Department.

Upon completion, the SAE Report Form must be immediately emailed or faxed to:

Pharmacovigilance Department
Karyopharm Therapeutics Inc.
Email: [contact]
[contact] (USA)

Any SAE observed after the 30-day follow-up period should only be reported to Karyopharm if the Investigator suspects that the SAE has a causal relationship to study treatment. Recurrent episodes, complications, or progression of the initial SAE must be reported as follow-up to the original episode within 24 hours of the Investigator receiving the follow-up information.

An SAE should be followed until its resolution or until it is judged to be permanent, and assessment should be made at each visit (or more frequently, if necessary) of any changes in severity of the event, the suspected relationship to the study treatment, the interventions required to treat the event, and the outcome.

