9.8.1. Adverse Events

Adverse Events (AEs) will be coded using the MedDRA dictionary and displayed in tables and listings using System/Organ/Class (SOC) and Preferred Term. Analyses of AEs will be performed for those events that are considered to be treatment-emergent AEs (TEAEs), defined as any AE with onset or worsening of a pre-existing condition on or after the first administration of study medication through 30 days following last dose or any event considered drug-related by the Investigator through the end of the study. Adverse events with partial dates will be assessed using the available date information to determine if treatment-emergent; AEs with completely missing dates will be assumed to be treatment-emergent.

Adverse events will be summarized by frequency counts at patient level. Tabulations will be provided for all TEAEs, for TEAEs assessed by the Investigator as at least possibly related to treatment, for \geq Grade 3 TEAEs, and for serious AEs (SAEs).

No formal hypothesis-testing analysis of AE incidence rates will be performed.

All AEs (treatment-emergent and post-treatment) will be listed in patient data listings. Separate by-patient listings will be provided for the following: patient deaths, SAEs, and AEs leading to withdrawal.

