# 1.7. MODIFICATIONS TO THE STATISTICAL SECTION OF THE PROTOCOL

The current SAP is based on Protocol Version 5.0 dated 1 March 2020. No modifications were made to the statistical section of the protocol.

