# 2.2.4. Handling of Missing Assessment of Relationship of AEs to Study Treatment

If the assessment of the relationship to study treatment is missing, then the relationship to study treatment in the frequency tables is considered as related.

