# **5.1.1.3.** Treatment-emergent Treatment-Related Adverse Events (TRAEs)

A TRAE is any TEAE that is related to any study treatment.

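### Table 20's two causality categories leave no proper place for possibly related events, although Protocol 9.8.1 plans to tabulate them and the SAP tabulates only related ones

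*Protocol*

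**What the plan says.** **Protocol 8.1.4, Table 20**, asks the investigator to choose one of two categories. Related applies when the timing "makes a definitive relationship, and the event is more likely explained by exposure to the study treatment than by any other drugs"; the same comparison covers causes that are not drugs. Not related applies when the lack of a temporal link "makes a causal relationship not reasonably possible, or other drugs, therapeutic interventions, or underlying conditions provide a sufficient explanation". There is no third category.

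**Protocol 9.8.1** promises separate tabulations, among them one "for TEAEs assessed by the Investigator as at least possibly related to treatment".

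**SAP 5.1.1.3** uses a different term: "A TRAE is any TEAE that is related to any study treatment". SAP 1.7 states that "No modifications were made to the statistical section of the protocol". SAP 2.2.4 adds that if the relationship is missing, "then the relationship to study treatment in the frequency tables is considered as related".

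**Protocol 6.2.6.2** attributes DLTs by a separate rule. It counts qualifying events "except for those that are clearly and incontrovertibly due to underlying disease, disease progression, or extraneous causes".

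**The concern.** A two-way causality question works only if every event belongs in one of the two answers. Here Related sets a high bar with two conditions that must both hold, while Not related can be met by either of two conditions. An event that may well be due to the drug, but cannot be tied to it definitively, has no proper place. In patients with advanced, progressing cancer, disease is often available as an explanation for terms such as anemia, fatigue or dyspnea, so such events are not rare edge cases.

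What is at stake is the treatment-related safety profile: the TRAE rows and by-causality tables of SAP 5.1.3 and 5.1.4, the related-death tables of SAP 5.2, and the status of late events. The trial has no control arm (Protocol 6.1.4), so there is no background rate against which a loss of related events would show.

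**Working it through.** **1. Classify four kinds of event under Table 20.** Related requires a definitive temporal link AND study treatment as the likelier explanation. Not related requires that causation is not reasonably possible OR that another cause suffices.

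| Event | Table 20 result | At least possibly related (9.8.1)? |
|---|---|---|
| a. Definitive timing, drug the likelier cause | Related | Yes |
| b. Timing rules the drug out | Not related | No |
| c. Plausible timing, no definitive link, no other sufficient cause | Neither | Yes |
| d. Plausible timing, no definitive link, disease would also suffice | Not related | Yes |

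The 9.8.1 table needs a, c and d. Table 20 reliably supplies only a. Type c has no category, and type d goes to the opposite one. So the 9.8.1 table cannot be built from the data that Table 20 defines.

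**2. Compare the protocol with the SAP.** Protocol Section 9 says that changes from its analyses will be described in the SAP. The SAP moves from at least possibly related (9.8.1) to related (5.1.1.3) and declares no change (1.7).

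**3. Trace what uses the flag.**
- It is used by the related-event, TRAE and related-death tables, and by late events. Protocol 9.8.1 and SAP 5.1.1.1 make an event after the treatment-emergent window a TEAE only if the investigator judges it related.
- It is not used by TEAE counts within the window, Grade 3 or higher AEs, SAEs or AEs leading to discontinuation. In the protocol synopsis the last three are primary endpoints without regard to causality.
- DLTs: the main rule has its own inclusive attribution test. Only the limb on more than 3 missed doses mentions drug-related toxicity, and it does not cite Table 20.
- Reporting: after the 30-day period an SAE "should only be reported to Karyopharm if the Investigator suspects that the SAE has a causal relationship to study treatment", which is a suspicion test. SUSARs (8.2.3) rest on the judgment of the investigator or the sponsor.

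**4. Scale.** The documents give no share of events of type c or d, so the effect cannot be estimated. What can be shown is how sensitive the rates are.
- The ten totals in Protocol Table 11 (treatment-related, N = 47) reproduce from their grade counts, for example anemia 2 + 7 + 22 + 1 = 32 and 32/47 = 68.1% (printed 68%); fatigue 15/47 = 31.9% (32%); AST increase 5/47 = 10.6% (11%).
- One reclassified patient moves a rate by 1/47 = 2.1 points. A term with 4/47 = 8.5% misses the 10% cut-off of that table, and one with 5/47 = 10.6% meets it.
- In a full Part C dose level of 10 patients, one patient is 1/10 = 10 points.
- Illustration on an assumption that is not in the documents: if a share f of at-least-possibly-related cases were coded Not related, the true count would be recorded/(1 − f). For a recorded 15/47 (31.9%), f = 0.10 gives 16.7/47 = 35.5% and f = 0.30 gives 21.4/47 = 45.6%.

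**The case against.** The strongest reply is the trial's own data. Table 11 attributes anemia to treatment in 68% of patients, fatigue in 32% and dyspnea in 17%, so investigators evidently did not assign these terms to disease by default. That stands as evidence against a large or uniform shift. It does not exclude a shift: the table shows only the events that were called related, and the documents do not say which causality wording applied to each.

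Second, the SAP uses the same word as Table 20, so a table of related events can be produced, and a blank relationship counts as related. Both points stand in part. The table that can be produced is not the one 9.8.1 promises. The missing-data rule may catch type c events if the site leaves the field blank, but not type d events that a site marks Not related by following the definition.

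Third, a reader might infer that toxicity has in fact been undercounted, or that dose finding and expedited reporting are pushed down as well. The documents do not support either. No count of affected events is given. DLTs are counted unless clearly due to something else, other events of concern may be declared DLTs, and dose decisions review all AEs (6.2.6.3). Every SAE up to 30 days is reported whatever its cause, later ones on suspicion, and the sponsor can classify a SUSAR independently. Nor is it a contradiction that an event may be a DLT without being Related: a deliberately cautious escalation rule can differ from causality coding.

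**Conclusion.** The defect is in the text and does not depend on any assumption: Table 20 is not exhaustive, its bar for Related is high, the 9.8.1 table cannot be derived from it, and the SAP's change of term is undeclared. An undercount in the related-TEAE and TRAE tables, and among late events that need a related judgment to become TEAEs, is the likely direction. That rests on sites applying Table 20 as written. Its size cannot be determined from the documents; the figures of 2.1 and 10 points describe sensitivity to one patient and are not estimates. The main safety conclusions are largely protected, because counts of Grade 3 or higher AEs, SAEs and discontinuations, TEAEs within the window and nearly all DLT decisions do not use the flag.

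**What to change.** - Redefine Table 20 as two complementary categories. Related: there is a reasonable possibility that study treatment caused or contributed to the event. Not related: there is no such possibility. State that another possible cause is not, by itself, enough for Not related.
- Use the same term in Protocol 9.8.1, SAP 5.1.1.3 and the eCRF guidance, and record the alignment in SAP 1.7.
- Report the date of the change, so that events attributed under the present wording can be identified.

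Re-attribution of events already entered is not required; in an open-label study it would invite hindsight.

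The cost is a wording amendment and a note to sites. Related-AE rates may become slightly less favourable, and attribution will not be uniform before and after the change, which the clinical study report should say.

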8.2. Serious Adverse Events

See Section 8.1.1 for the definition of an SAE. Please note that SAEs that occur at any time between the signing of the ICF up to the first dose of study treatment, must be reported (in addition to SAEs that occur after the first dose of study treatment).

Important medical events that may not result in death, are not life-threatening, or do not require hospitalization may be considered SAEs when, based on appropriate medical judgment, they may jeopardize the patient and may require medical or surgical intervention to prevent 1 of the outcomes listed in this definition. Examples of such events include allergic bronchospasm requiring intensive treatment in an emergency room or at home, blood dyscrasias or convulsions that do not result in in-patient hospitalization, or the development of drug dependency or drug abuse.

Hospitalizations for elective surgery or other medical procedures that are not due to an AE are not considered SAEs. A hospitalization meeting the regulatory definition for ‘serious’ is any inpatient hospital admission that includes a minimum of an overnight stay in a health care facility. An emergency room visit is not considered a hospitalization unless it results in an official admission to the hospital.

Progression of the malignancy (including fatal outcomes) should not be reported as an SAE during the study or within the safety reporting period (see Section 8.2.2). Sudden and unexplained death should be reported as an SAE. If there is any uncertainty about a finding being due solely to progression of malignancy, the finding should be reported as an AE or SAE, as appropriate.

8.2.1. Recording of Serious Adverse Events

It is the responsibility of the Investigator to record and document all SAEs occurring from the signing of the ICF until at least 30 days after the patient has stopped study treatment. All SAEs must be reported on an SAE report form, in addition to being recorded in the eCRF. The original SAE report form must be retained in the Investigator’s site file.

All applicable sections of the form must be completed in order to provide a clinically thorough report. The Investigator must assess and record the relationship of each SAE to study treatment and complete the SAE Report Form (in English).

See ICH E2A (Clinical Safety Data Management: Definitions and Standards for Expedited Reporting, Attachment 1) for key data elements that are required for expedited reporting.

8.2.2. Reporting of Serious Adverse Events

Every SAE, regardless of the causal relationship to the study treatment, occurring after the patient has signed informed consent, until at least 30 days after the patient has stopped study treatment, must be reported to the Karyopharm Pharmacovigilance Department within *24 hours* of learning of its occurrence. The investigational site personnel must use the SAE Report Form provided by Karyopharm for reporting any SAE to the Karyopharm Pharmacovigilance Department.

Upon completion, the SAE Report Form must be immediately emailed or faxed to:

Pharmacovigilance Department
Karyopharm Therapeutics Inc.
Email: [contact]
[contact] (USA)

Any SAE observed after the 30-day follow-up period should only be reported to Karyopharm if the Investigator suspects that the SAE has a causal relationship to study treatment. Recurrent episodes, complications, or progression of the initial SAE must be reported as follow-up to the original episode within 24 hours of the Investigator receiving the follow-up information.

An SAE should be followed until its resolution or until it is judged to be permanent, and assessment should be made at each visit (or more frequently, if necessary) of any changes in severity of the event, the suspected relationship to the study treatment, the interventions required to treat the event, and the outcome.

8.2.3. Suspected Unexpected Serious Adverse Reactions

Suspected unexpected serious adverse reactions (SUSARs) are SAEs that are unexpected and judged by the Investigator or Karyopharm to be related to the study treatment administered. SUSARs will be collected and reported to the competent authorities and relevant ethics committees in accordance with the FDA's "Safety Reporting Requirements for Investigational New Drugs and Bioanalytical/Bioequivalence Studies" or as per national regulatory requirements in participating countries.

In addition, Karyopharm will communicate all cases of cerebellar toxicity, Grade 3 or higher, to regulatory authorities, central ethics committees (e.g., IRBs), and Investigators, in the format of an expedited Safety Report, within 7 days of awareness of the event.

If required by local regulations, the Investigator is responsible for notifying his/her IRB or local ethics committee of all SAEs.

8.3. Procedures for Handling Special Situations

8.3.1. Pregnancy

Note: Pregnancy *per se* is not considered to be an AE; however, it is discussed here because of the importance of reporting pregnancies that occur during studies and because a medical occurrence observed in the mother or fetus/newborn would be classified as an AE.

To ensure patient safety, a pregnancy occurring while the patient is on study treatment must be reported to Karyopharm Pharmacovigilance by email or fax within 24 hours of first knowledge of its occurrence. A pregnancy report form is provided by Karyopharm.

The pregnancy should be followed up to determine outcome, including spontaneous or voluntary termination, details of the birth, and the presence or absence of any birth defects, congenital abnormalities, or maternal and/or newborn complications.

Pregnancies must be reported to Karyopharm, regardless of whether the patient withdraws from the study or the study is completed, for 3 months after the patient receives his/her last dose of study treatment. Patients should be instructed to inform the Investigator regarding any pregnancies.

Any SAE that occurs during pregnancy must be recorded on the SAE report form (e.g., maternal serious complications, therapeutic abortion, ectopic pregnancy, stillbirth, neonatal death, congenital anomaly, birth defect) and reported within 24 hours in accordance with the procedure for reporting SAEs.

A pregnancy in a female partner of a male patient must be reported to Karyopharm within 24 hours of learning of its occurrence. Pregnancies in female partners should only be followed if the male patient is being treated with a KPT-9274-containing regimen.

8.3.2. Abuse, Misuse, Medication Errors, Overdose, and Occupational Exposure

All incidences of abuse, misuse, medication errors, overdose, and occupational exposure are required to be reported to Karyopharm Pharmacovigilance on an SAE report form, faxed to [contact], regardless of whether or not there is an associated AE or SAE.

8.3.2.1. Overdose

An overdose is a deliberate or accidental administration of any study treatment to a study patient, at a dose greater than that which was assigned to that patient per the study protocol. If an overdose occurs, the Investigator and Karyopharm should be notified immediately, and the patient should be observed closely for AEs. Resulting symptoms should be treated, as appropriate, and the incident of overdose and related AEs and/or treatment should be documented in the patient's medical record and in the eCRF. Overdose is to be reported on an SAE report form to Karyopharm Pharmacovigilance regardless of whether or not an AE or SAE has occurred due to the overdose. If the overdose is associated with an SAE, the SAE report form must be submitted to Karyopharm Pharmacovigilance within 24 hours of awareness. If there is no AE or SAE, the report must be submitted as soon as possible.

